14.3 Safety Data

14.3.1 Displays of Adverse Events

Table 38: Overall Summary of Adverse Events – Safety Population*

Subjects ^a with	M2SR (N=X)		Placebo (N=X)		All Subjects (N=X)	
	n	%	n	%	n	%
At least one local solicited adverse event	x	x	x	x	x	x
Mild (Grade 1)	x	x	x	x	x	x
Moderate (Grade 2)	x	x	x	x	x	x
Severe (Grade 3)	x	x	x	x	x	x
At least one systemic solicited adverse event	x	x	x	x	x	x
Mild (Grade 1)	x	x	x	x	x	x
Moderate (Grade 2)	x	x	x	x	x	x
Severe (Grade 3)	x	x	x	x	x	x
At least one unsolicited adverse event	x	x	x	x	x	x
At least one related unsolicited adverse event	x	x	x	x	x	x
Mild (Grade 1)	x	x	x	x	x	x
Moderate (Grade 2)	x	x	x	x	x	x
Severe (Grade 3)	x	x	x	x	x	x
Not yet assessed						

Table 38: Overall Summary of Adverse Events – Safety Population* (Continued)

	M2SR (N=X)		Placebo (N=X)		All Subjects (N=X)	
	n	%	n	%	n	%
Subjects^a with						
At least one severe (Grade 3) unsolicited adverse event	x	x	x	x	x	x
Related	x	x	x	x	x	x
Unrelated	x	x	x	x	x	x
At least one serious adverse event ^b	x	x	x	x	x	x
At least one related, serious adverse event	x	x	x	x	x	x
At least one adverse event leading to early termination ^c	x	x	x	x	x	x
At least one adverse event of special interest	x	x	x	x	x	x
At least one new onset chronic medical condition	x	x	x	x	x	x
N = Number of subjects in the Safety Population ^a Subjects are counted once for each category regardless of the number of events. ^b A listing of Serious Adverse Events is included in Table X. ^c As reported on the Adverse Event eCRF.						

Table 39: Adverse Events Occurring in 5% of Subjects in Any Study Group by MedDRA System Organ Class and Preferred Term, and Study Arm - Safety Population

Preferred Term	MedDRA System Organ Class	M2SR (N=X)			Placebo (N=X)			All Subjects (N=X)		
		n	%	Events	n	%	Events	n	%	Events
Serious Adverse Events										
All	All	x	x	x	x	x	x	x	x	x
PT1	SOC1	x	x	x	x	x	x	x	x	x
Etc.	Etc.									
Other (Non-serious) Adverse Events										
All	All	x	x	x	x	x	x	x	x	x
PT1	SOC1	x	x	x	x	x	x	x	x	x
Etc.	Etc.									
N = number of subjects in the Safety Population (number of subjects at risk). n= number of subjects reporting event. Events= total frequency of events reported.										

14.3.1.1 Solicited Adverse Events

Table 40: Number and Percentage of Subjects Experiencing Solicited Events Post First Vaccination with 95% Confidence Intervals by Symptom and Study Group – Safety Population

Symptom	M2SR (N=X)			Placebo (N=X)		
	n	%	95% CI	n	%	95% CI
Any Symptom	x	xx	x.x, x.x	x	xx	x.x, x.x
Systemic Symptoms						
Any Systemic Symptom	x	xx	x.x, x.x	x	xx	x.x, x.x
Feverishness (Chills/Shivering/Sweating)	x	xx	x.x, x.x	x	xx	x.x, x.x
Fatigue (Tiredness)	x	xx	x.x, x.x	x	xx	x.x, x.x
Malaise (General Unwell Feeling)	x	xx	x.x, x.x	x	xx	x.x, x.x
Myalgia (Body Aches/Muscular Pain)	x	xx	x.x, x.x	x	xx	x.x, x.x
Arthralgia (Joint Pain)	x	xx	x.x, x.x	x	xx	x.x, x.x
Headache	x	xx	x.x, x.x	x	xx	x.x, x.x
Flushing	x	xx	x.x, x.x	x	xx	x.x, x.x
Decreased Activity	x	xx	x.x, x.x	x	xx	x.x, x.x
Decreased Appetite	x	xx	x.x, x.x	x	xx	x.x, x.x
Abdominal Pain	x	xx	x.x, x.x	x	xx	x.x, x.x
Nausea	x	xx	x.x, x.x	x	xx	x.x, x.x
Vomiting	x	xx	x.x, x.x	x	xx	x.x, x.x
Diarrhea	x	xx	x.x, x.x	x	xx	x.x, x.x
Eye Pruritus	x	xx	x.x, x.x	x	xx	x.x, x.x
Eye Redness (Conjunctivitis)	x	xx	x.x, x.x	x	xx	x.x, x.x
Allergy	x	xx	x.x, x.x	x	xx	x.x, x.x
Wheezing	x	xx	x.x, x.x	x	xx	x.x, x.x

Table 40: Number and Percentage of Subjects Experiencing Solicited Events Post First Vaccination with 95% Confidence Intervals by Symptom and Study Group – Safety Population (Continued)

Symptom	M2SR (N=X)			Placebo (N=X)		
	n	%	95% CI	n	%	95% CI
Local Symptoms						
Any Local Symptom	x	xx	x.x, x.x	x	xx	x.x, x.x
Runny Nose	x	xx	x.x, x.x	x	xx	x.x, x.x
Stuffy Nose/Congestion	x	xx	x.x, x.x	x	xx	x.x, x.x
Sneezing	x	xx	x.x, x.x	x	xx	x.x, x.x
Nasal Pain/Irritation	x	xx	x.x, x.x	x	xx	x.x, x.x
Nasal Bleeding/Epistaxis	x	xx	x.x, x.x	x	xx	x.x, x.x
Sinus Pressure/Pain	x	xx	x.x, x.x	x	xx	x.x, x.x
Sore Throat/Sore/Scratchy/Itchy or Painful Throat	x	xx	x.x, x.x	x	xx	x.x, x.x
Cough	x	xx	x.x, x.x	x	xx	x.x, x.x
Trouble Breathing/Shortness of Breath	x	xx	x.x, x.x	x	xx	x.x, x.x
Note: N= Number of subjects in the Safety Population						

Table 41: Comparison of the Proportion of Subjects Experiencing Solicited Events by Study Group

Symptom	Proportion (95% CI)		Difference (95% CI)
	M2SR (N=X)	Placebo (N=X)	
Any Symptom	x.xx (x.xx, x.xx)	x.xx (x.xx, x.xx)	x.xx (x.xx, x.xx)
Systemic Symptoms			
Any Systemic Symptom	x.xx (x.xx, x.xx)	x.xx (x.xx, x.xx)	x.xx (x.xx, x.xx)
Feverishness (Chills/Shivering/Sweating)	x.xx (x.xx, x.xx)	x.xx (x.xx, x.xx)	x.xx (x.xx, x.xx)
Fatigue (Tiredness)	x.xx (x.xx, x.xx)	x.xx (x.xx, x.xx)	x.xx (x.xx, x.xx)
Malaise (General Unwell Feeling)	x.xx (x.xx, x.xx)	x.xx (x.xx, x.xx)	x.xx (x.xx, x.xx)
Myalgia (Body Aches/Muscular Pain)	x.xx (x.xx, x.xx)	x.xx (x.xx, x.xx)	x.xx (x.xx, x.xx)
Arthralgia (Joint Pain)	x.xx (x.xx, x.xx)	x.xx (x.xx, x.xx)	x.xx (x.xx, x.xx)
Headache	x.xx (x.xx, x.xx)	x.xx (x.xx, x.xx)	x.xx (x.xx, x.xx)
Flushing	x.xx (x.xx, x.xx)	x.xx (x.xx, x.xx)	x.xx (x.xx, x.xx)
Decreased Activity	x.xx (x.xx, x.xx)	x.xx (x.xx, x.xx)	x.xx (x.xx, x.xx)
Decreased Appetite	x.xx (x.xx, x.xx)	x.xx (x.xx, x.xx)	x.xx (x.xx, x.xx)
Abdominal Pain	x.xx (x.xx, x.xx)	x.xx (x.xx, x.xx)	x.xx (x.xx, x.xx)
Nausea	x.xx (x.xx, x.xx)	x.xx (x.xx, x.xx)	x.xx (x.xx, x.xx)
Vomiting	x.xx (x.xx, x.xx)	x.xx (x.xx, x.xx)	x.xx (x.xx, x.xx)
Diarrhea	x.xx (x.xx, x.xx)	x.xx (x.xx, x.xx)	x.xx (x.xx, x.xx)
Eye Pruritus	x.xx (x.xx, x.xx)	x.xx (x.xx, x.xx)	x.xx (x.xx, x.xx)
Eye Redness (Conjunctivitis)	x.xx (x.xx, x.xx)	x.xx (x.xx, x.xx)	x.xx (x.xx, x.xx)
Allergy	x.xx (x.xx, x.xx)	x.xx (x.xx, x.xx)	x.xx (x.xx, x.xx)
Wheezing	x.xx (x.xx, x.xx)	x.xx (x.xx, x.xx)	x.xx (x.xx, x.xx)

Table 41: Comparison of the Proportion of Subjects Experiencing Solicited Events by Study Group (Continued)

Symptom	Proportion (95% CI)		Difference (95% CI)
	M2SR (N=X)	Placebo (N=X)	
Local Symptoms			
Any Local Symptom	x.xx (x.xx, x.xx)	x.xx (x.xx, x.xx)	x.xx (x.xx, x.xx)
Runny Nose	x.xx (x.xx, x.xx)	x.xx (x.xx, x.xx)	x.xx (x.xx, x.xx)
Stuffy Nose/Congestion	x.xx (x.xx, x.xx)	x.xx (x.xx, x.xx)	x.xx (x.xx, x.xx)
Sneezing	x.xx (x.xx, x.xx)	x.xx (x.xx, x.xx)	x.xx (x.xx, x.xx)
Nasal Pain/Irritation	x.xx (x.xx, x.xx)	x.xx (x.xx, x.xx)	x.xx (x.xx, x.xx)
Nasal Bleeding/Epistaxis	x.xx (x.xx, x.xx)	x.xx (x.xx, x.xx)	x.xx (x.xx, x.xx)
Sinus Pressure/Pain	x.xx (x.xx, x.xx)	x.xx (x.xx, x.xx)	x.xx (x.xx, x.xx)
Sore Throat/Sore/Scratchy/Itchy or Painful Throat	x.xx (x.xx, x.xx)	x.xx (x.xx, x.xx)	x.xx (x.xx, x.xx)
Cough	x.xx (x.xx, x.xx)	x.xx (x.xx, x.xx)	x.xx (x.xx, x.xx)
Trouble Breathing/Shortness of Breath	x.xx (x.xx, x.xx)	x.xx (x.xx, x.xx)	x.xx (x.xx, x.xx)
Note: N = Number of subjects in the Safety Population			

Table 42: Number and Percentage of Subjects Experiencing Solicited Events by Symptom, Maximum Severity, and Study Group - Safety Population

Symptom	Severity	M2SR (N=X)			Placebo (N=X)		
		n	%	95% CI	n	%	95% CI
Any Symptom	None	x	xx	x.x, x.x	x	xx	x.x, x.x
	Mild	x	xx	xx,xx	x	xx	xx,xx
	Moderate	x	xx	xx,xx	x	xx	xx,xx
	Severe	x	xx	xx,xx	x	xx	xx,xx
Systemic Symptoms							
Any Systemic Symptom	None	x	xx	xx,xx	x	xx	xx,xx
	Mild	x	xx	xx,xx	x	xx	xx,xx
	Moderate	x	xx	xx,xx	x	xx	xx,xx
	Severe	x	xx	xx,xx	x	xx	xx,xx
Feverishness (Chills/Shivering/Sweating)	None	x	xx	xx,xx	x	xx	xx,xx
	Mild	x	xx	xx,xx	x	xx	xx,xx
	Moderate	x	xx	xx,xx	x	xx	xx,xx
	Severe	x	xx	xx,xx	x	xx	xx,xx
Fatigue (Tiredness)	None	x	xx	xx,xx	x	xx	xx,xx
	Mild	x	xx	xx,xx	x	xx	xx,xx
	Moderate	x	xx	xx,xx	x	xx	xx,xx
	Severe	x	xx	xx,xx	x	xx	xx,xx
Malaise (General Unwell Feeling)	None	x	xx	xx,xx	x	xx	xx,xx
	Mild	x	xx	xx,xx	x	xx	xx,xx
	Moderate	x	xx	xx,xx	x	xx	xx,xx
	Severe	x	xx	xx,xx	x	xx	xx,xx

Table 42: Number and Percentage of Subjects Experiencing Solicited Events by Symptom, Maximum Severity, and Study Group - Safety Population (Continued)

Symptom	Severity	M2SR (N=X)			Placebo (N=X)		
		n	%	95% CI	n	%	95% CI
Myalgia (Body Aches/Muscular Pain)	None	x	xx	xx,xx	x	xx	xx,xx
	Mild	x	xx	xx,xx	x	xx	xx,xx
	Moderate	x	xx	xx,xx	x	xx	xx,xx
	Severe	x	xx	xx,xx	x	xx	xx,xx
Arthralgia (Joint Pain)	None	x	xx	xx,xx	x	xx	xx,xx
	Mild	x	xx	xx,xx	x	xx	xx,xx
	Moderate	x	xx	xx,xx	x	xx	xx,xx
	Severe	x	xx	xx,xx	x	xx	xx,xx
Headache	None	x	xx	xx,xx	x	xx	xx,xx
	Mild	x	xx	xx,xx	x	xx	xx,xx
	Moderate	x	xx	xx,xx	x	xx	xx,xx
	Severe	x	xx	xx,xx	x	xx	xx,xx
Flushing	None	x	xx	xx,xx	x	xx	xx,xx
	Mild	x	xx	xx,xx	x	xx	xx,xx
	Moderate	x	xx	xx,xx	x	xx	xx,xx
	Severe	x	xx	xx,xx	x	xx	xx,xx
Decreased Activity	None	x	xx	xx,xx	x	xx	xx,xx
	Mild	x	xx	xx,xx	x	xx	xx,xx
	Moderate	x	xx	xx,xx	x	xx	xx,xx
	Severe	x	xx	xx,xx	x	xx	xx,xx
Decreased Appetite	None	x	xx	xx,xx	x	xx	xx,xx
	Mild	x	xx	xx,xx	x	xx	xx,xx

Table 42: Number and Percentage of Subjects Experiencing Solicited Events by Symptom, Maximum Severity, and Study Group - Safety Population (Continued)

Symptom	Severity	M2SR (N=X)			Placebo (N=X)		
		n	%	95% CI	n	%	95% CI
	Moderate	x	xx	xx,xx	x	xx	xx,xx
	Severe	x	xx	xx,xx	x	xx	xx,xx
Abdominal Pain	None	x	xx	xx,xx	x	xx	xx,xx
	Mild	x	xx	xx,xx	x	xx	xx,xx
	Moderate	x	xx	xx,xx	x	xx	xx,xx
	Severe	x	xx	xx,xx	x	xx	xx,xx
Nausea	None	x	xx	xx,xx	x	xx	xx,xx
	Mild	x	xx	xx,xx	x	xx	xx,xx
	Moderate	x	xx	xx,xx	x	xx	xx,xx
	Severe	x	xx	xx,xx	x	xx	xx,xx
Vomiting	None	x	xx	xx,xx	x	xx	xx,xx
	Mild	x	xx	xx,xx	x	xx	xx,xx
	Moderate	x	xx	xx,xx	x	xx	xx,xx
	Severe	x	xx	xx,xx	x	xx	xx,xx
Diarrhea	None	x	xx	xx,xx	x	xx	xx,xx
	Mild	x	xx	xx,xx	x	xx	xx,xx
	Moderate	x	xx	xx,xx	x	xx	xx,xx
	Severe	x	xx	xx,xx	x	xx	xx,xx
Eye Pruritus	None	x	xx	xx,xx	x	xx	xx,xx
	Mild	x	xx	xx,xx	x	xx	xx,xx
	Moderate	x	xx	xx,xx	x	xx	xx,xx
	Severe	x	xx	xx,xx	x	xx	xx,xx

Table 42: Number and Percentage of Subjects Experiencing Solicited Events by Symptom, Maximum Severity, and Study Group - Safety Population (Continued)

Symptom	Severity	M2SR (N=X)			Placebo (N=X)		
		n	%	95% CI	n	%	95% CI
Eye Redness (Conjunctivitis)	None	x	xx	xx,xx	x	xx	xx,xx
	Mild	x	xx	xx,xx	x	xx	xx,xx
	Moderate	x	xx	xx,xx	x	xx	xx,xx
	Severe	x	xx	xx,xx	x	xx	xx,xx
Allergy	None	x	xx	xx,xx	x	xx	xx,xx
	Mild	x	xx	xx,xx	x	xx	xx,xx
	Moderate	x	xx	xx,xx	x	xx	xx,xx
	Severe	x	xx	xx,xx	x	xx	xx,xx
Wheezing	None	x	xx	xx,xx	x	xx	xx,xx
	Mild	x	xx	xx,xx	x	xx	xx,xx
	Moderate	x	xx	xx,xx	x	xx	xx,xx
	Severe	x	xx	xx,xx	x	xx	xx,xx
Local Symptoms							
Any Local Symptom	None	x	xx	xx,xx	x	xx	xx,xx
	Mild	x	xx	xx,xx	x	xx	xx,xx
	Moderate	x	xx	xx,xx	x	xx	xx,xx
	Severe	x	xx	xx,xx	x	xx	xx,xx
Runny Nose	None	x	xx	xx,xx	x	xx	xx,xx
	Mild	x	xx	xx,xx	x	xx	xx,xx
	Moderate	x	xx	xx,xx	x	xx	xx,xx
	Severe	x	xx	xx,xx	x	xx	xx,xx

Table 42: Number and Percentage of Subjects Experiencing Solicited Events by Symptom, Maximum Severity, and Study Group - Safety Population (Continued)

Symptom	Severity	M2SR (N=X)			Placebo (N=X)		
		n	%	95% CI	n	%	95% CI
Stuffy Nose/Congestion	None	x	xx	xx,xx	x	xx	xx,xx
	Mild	x	xx	xx,xx	x	xx	xx,xx
	Moderate	x	xx	xx,xx	x	xx	xx,xx
	Severe	x	xx	xx,xx	x	xx	xx,xx
Sneezing	None	x	xx	xx,xx	x	xx	xx,xx
	Mild	x	xx	xx,xx	x	xx	xx,xx
	Moderate	x	xx	xx,xx	x	xx	xx,xx
	Severe	x	xx	xx,xx	x	xx	xx,xx
Nasal Pain/Irritation	None	x	xx	xx,xx	x	xx	xx,xx
	Mild	x	xx	xx,xx	x	xx	xx,xx
	Moderate	x	xx	xx,xx	x	xx	xx,xx
	Severe	x	xx	xx,xx	x	xx	xx,xx
Nasal Bleeding/Epistaxis	None	x	xx	xx,xx	x	xx	xx,xx
	Mild	x	xx	xx,xx	x	xx	xx,xx
	Moderate	x	xx	xx,xx	x	xx	xx,xx
	Severe	x	xx	xx,xx	x	xx	xx,xx
Sinus Pressure/Pain	None	x	xx	xx,xx	x	xx	xx,xx
	Mild	x	xx	xx,xx	x	xx	xx,xx
	Moderate	x	xx	xx,xx	x	xx	xx,xx
	Severe	x	xx	xx,xx	x	xx	xx,xx

Table 42: Number and Percentage of Subjects Experiencing Solicited Events by Symptom, Maximum Severity, and Study Group - Safety Population (Continued)

Symptom	Severity	M2SR (N=X)			Placebo (N=X)		
		n	%	95% CI	n	%	95% CI
Sore Throat/Sore/Scratchy/Itchy or Painful Throat	None	x	xx	xx,xx	x	xx	xx,xx
	Mild	x	xx	xx,xx	x	xx	xx,xx
	Moderate	x	xx	xx,xx	x	xx	xx,xx
	Severe	x	xx	xx,xx	x	xx	xx,xx
Cough	None	x	xx	xx,xx	x	xx	xx,xx
	Mild	x	xx	xx,xx	x	xx	xx,xx
	Moderate	x	xx	xx,xx	x	xx	xx,xx
	Severe	x	xx	xx,xx	x	xx	xx,xx
Trouble Breathing/Shortness of Breath	None	x	xx	xx,xx	x	xx	xx,xx
	Mild	x	xx	xx,xx	x	xx	xx,xx
	Moderate	x	xx	xx,xx	x	xx	xx,xx
	Severe	x	xx	xx,xx	x	xx	xx,xx

Note: N = Number of subjects in the Safety Population. Severity is the maximum severity reported over all solicited symptoms post dosing for each subject.

Table 43: Number and Percentage of Subjects Experiencing Solicited Events by Symptom, Severity and Day Post First Vaccination – M2SR Recipients, Safety Population

Symptom	Severity	Pre-Dose		Post-Dose		Day 1		Day 2		Day 3		Day 4		Day 5		Day 6		Day 7		Day 8+	
		n	%	n	%	n	%	n	%	n	%	n	%	n	%	n	%	n	%	n	%
Any Symptom	None	x	xx	x	xx	x	xx	x	xx	x	xx	x	xx	x	xx	x	xx	x	xx	x	xx
	Mild	x	xx	x	xx	x	xx	x	xx	x	xx	x	xx	x	xx	x	xx	x	xx	x	xx
	Moderate	x	xx	x	xx	x	xx	x	xx	x	xx	x	xx	x	xx	x	xx	x	xx	x	xx
	Severe	x	xx	x	xx	x	xx	x	xx	x	xx	x	xx	x	xx	x	xx	x	xx	x	xx
	Not Reported	x	xx	x	xx	x	xx	x	xx	x	xx	x	xx	x	xx	x	xx	x	xx	x	xx
Systemic Symptoms																					
Any Systemic Symptom	None	x	xx	x	xx	x	xx	x	xx	x	xx	x	xx	x	xx	x	xx	x	xx	x	xx
	Mild	x	xx	x	xx	x	xx	x	xx	x	xx	x	xx	x	xx	x	xx	x	xx	x	xx
	Moderate	x	xx	x	xx	x	xx	x	xx	x	xx	x	xx	x	xx	x	xx	x	xx	x	xx
	Severe	x	xx	x	xx	x	xx	x	xx	x	xx	x	xx	x	xx	x	xx	x	xx	x	xx
	Not Reported	x	xx	x	xx	x	xx	x	xx	x	xx	x	xx	x	xx	x	xx	x	xx	x	xx
Feverishness (Chills/Shivering/Sweating)	None	x	xx	x	xx	x	xx	x	xx	x	xx	x	xx	x	xx	x	xx	x	xx	x	xx
	Mild	x	xx	x	xx	x	xx	x	xx	x	xx	x	xx	x	xx	x	xx	x	xx	x	xx
	Moderate	x	xx	x	xx	x	xx	x	xx	x	xx	x	xx	x	xx	x	xx	x	xx	x	xx
	Severe	x	xx	x	xx	x	xx	x	xx	x	xx	x	xx	x	xx	x	xx	x	xx	x	xx
	Not Reported	x	xx	x	xx	x	xx	x	xx	x	xx	x	xx	x	xx	x	xx	x	xx	x	xx
Fatigue (Tiredness)	None	x	xx	x	xx	x	xx	x	xx	x	xx	x	xx	x	xx	x	xx	x	xx	x	xx
	Mild	x	xx	x	xx	x	xx	x	xx	x	xx	x	xx	x	xx	x	xx	x	xx	x	xx
	Moderate	x	xx	x	xx	x	xx	x	xx	x	xx	x	xx	x	xx	x	xx	x	xx	x	xx

Table 43: Number and Percentage of Subjects Experiencing Solicited Events by Symptom, Severity and Day Post First Vaccination – M2SR Recipients, Safety Population (Continued)

Symptom	Severity	Pre-Dose		Post-Dose		Day 1		Day 2		Day 3		Day 4		Day 5		Day 6		Day 7		Day 8+	
		n	%	n	%	n	%	n	%	n	%	n	%	n	%	n	%	n	%	n	%
	Severe	x	xx	x	xx	x	xx	x	xx	x	xx	x	xx	x	xx	x	xx	x	xx	x	xx
	Not Reported	x	xx	x	xx	x	xx	x	xx	x	xx	x	xx	x	xx	x	xx	x	xx	x	xx
Malaise (General Unwell Feeling)	None	x	xx	x	xx	x	xx	x	xx	x	xx	x	xx	x	xx	x	xx	x	xx	x	xx
	Mild	x	xx	x	xx	x	xx	x	xx	x	xx	x	xx	x	xx	x	xx	x	xx	x	xx
	Moderate	x	xx	x	xx	x	xx	x	xx	x	xx	x	xx	x	xx	x	xx	x	xx	x	xx
	Severe	x	xx	x	xx	x	xx	x	xx	x	xx	x	xx	x	xx	x	xx	x	xx	x	xx
	Not Reported	x	xx	x	xx	x	xx	x	xx	x	xx	x	xx	x	xx	x	xx	x	xx	x	xx
Myalgia (Body Aches/Muscular Pain)	None	x	xx	x	xx	x	xx	x	xx	x	xx	x	xx	x	xx	x	xx	x	xx	x	xx
	Mild	x	xx	x	xx	x	xx	x	xx	x	xx	x	xx	x	xx	x	xx	x	xx	x	xx
	Moderate	x	xx	x	xx	x	xx	x	xx	x	xx	x	xx	x	xx	x	xx	x	xx	x	xx
	Severe	x	xx	x	xx	x	xx	x	xx	x	xx	x	xx	x	xx	x	xx	x	xx	x	xx
	Not Reported	x	xx	x	xx	x	xx	x	xx	x	xx	x	xx	x	xx	x	xx	x	xx	x	xx
Arthralgia (Joint Pain)	None	x	xx	x	xx	x	xx	x	xx	x	xx	x	xx	x	xx	x	xx	x	xx	x	xx
	Mild	x	xx	x	xx	x	xx	x	xx	x	xx	x	xx	x	xx	x	xx	x	xx	x	xx
	Moderate	x	xx	x	xx	x	xx	x	xx	x	xx	x	xx	x	xx	x	xx	x	xx	x	xx
	Severe	x	xx	x	xx	x	xx	x	xx	x	xx	x	xx	x	xx	x	xx	x	xx	x	xx
	Not Reported	x	xx	x	xx	x	xx	x	xx	x	xx	x	xx	x	xx	x	xx	x	xx	x	xx
Headache	None	x	xx	x	xx	x	xx	x	xx	x	xx	x	xx	x	xx	x	xx	x	xx	x	xx
	Mild	x	xx	x	xx	x	xx	x	xx	x	xx	x	xx	x	xx	x	xx	x	xx	x	xx
	Moderate	x	xx	x	xx	x	xx	x	xx	x	xx	x	xx	x	xx	x	xx	x	xx	x	xx

Table 43: Number and Percentage of Subjects Experiencing Solicited Events by Symptom, Severity and Day Post First Vaccination – M2SR Recipients, Safety Population (Continued)

Symptom	Severity	Pre-Dose		Post-Dose		Day 1		Day 2		Day 3		Day 4		Day 5		Day 6		Day 7		Day 8+	
		n	%	n	%	n	%	n	%	n	%	n	%	n	%	n	%	n	%	n	%
	Severe	x	xx	x	xx	x	xx	x	xx	x	xx	x	xx	x	xx	x	xx	x	xx	x	xx
	Not Reported	x	xx	x	xx	x	xx	x	xx	x	xx	x	xx	x	xx	x	xx	x	xx	x	xx
Flushing	None	x	xx	x	xx	x	xx	x	xx	x	xx	x	xx	x	xx	x	xx	x	xx	x	xx
	Mild	x	xx	x	xx	x	xx	x	xx	x	xx	x	xx	x	xx	x	xx	x	xx	x	xx
	Moderate	x	xx	x	xx	x	xx	x	xx	x	xx	x	xx	x	xx	x	xx	x	xx	x	xx
	Severe	x	xx	x	xx	x	xx	x	xx	x	xx	x	xx	x	xx	x	xx	x	xx	x	xx
	Not Reported	x	xx	x	xx	x	xx	x	xx	x	xx	x	xx	x	xx	x	xx	x	xx	x	xx
Decreased Activity	None	x	xx	x	xx	x	xx	x	xx	x	xx	x	xx	x	xx	x	xx	x	xx	x	xx
	Mild	x	xx	x	xx	x	xx	x	xx	x	xx	x	xx	x	xx	x	xx	x	xx	x	xx
	Moderate	x	xx	x	xx	x	xx	x	xx	x	xx	x	xx	x	xx	x	xx	x	xx	x	xx
	Severe	x	xx	x	xx	x	xx	x	xx	x	xx	x	xx	x	xx	x	xx	x	xx	x	xx
	Not Reported	x	xx	x	xx	x	xx	x	xx	x	xx	x	xx	x	xx	x	xx	x	xx	x	xx
Decreased Appetite	None	x	xx	x	xx	x	xx	x	xx	x	xx	x	xx	x	xx	x	xx	x	xx	x	xx
	Mild	x	xx	x	xx	x	xx	x	xx	x	xx	x	xx	x	xx	x	xx	x	xx	x	xx
	Moderate	x	xx	x	xx	x	xx	x	xx	x	xx	x	xx	x	xx	x	xx	x	xx	x	xx
	Severe	x	xx	x	xx	x	xx	x	xx	x	xx	x	xx	x	xx	x	xx	x	xx	x	xx
	Not Reported	x	xx	x	xx	x	xx	x	xx	x	xx	x	xx	x	xx	x	xx	x	xx	x	xx
Abdominal Pain	None	x	xx	x	xx	x	xx	x	xx	x	xx	x	xx	x	xx	x	xx	x	xx	x	xx
	Mild	x	xx	x	xx	x	xx	x	xx	x	xx	x	xx	x	xx	x	xx	x	xx	x	xx
	Moderate	x	xx	x	xx	x	xx	x	xx	x	xx	x	xx	x	xx	x	xx	x	xx	x	xx
	Severe	x	xx	x	xx	x	xx	x	xx	x	xx	x	xx	x	xx	x	xx	x	xx	x	xx

Table 43: Number and Percentage of Subjects Experiencing Solicited Events by Symptom, Severity and Day Post First Vaccination – M2SR Recipients, Safety Population (Continued)

Symptom	Severity	Pre-Dose		Post-Dose		Day 1		Day 2		Day 3		Day 4		Day 5		Day 6		Day 7		Day 8+	
		n	%	n	%	n	%	n	%	n	%	n	%	n	%	n	%	n	%	n	%
	Not Reported	x	xx	x	xx	x	xx	x	xx	x	xx	x	xx	x	xx	x	xx	x	xx	x	xx
Nausea	None	x	xx	x	xx	x	xx	x	xx	x	xx	x	xx	x	xx	x	xx	x	xx	x	xx
	Mild	x	xx	x	xx	x	xx	x	xx	x	xx	x	xx	x	xx	x	xx	x	xx	x	xx
	Moderate	x	xx	x	xx	x	xx	x	xx	x	xx	x	xx	x	xx	x	xx	x	xx	x	xx
	Severe	x	xx	x	xx	x	xx	x	xx	x	xx	x	xx	x	xx	x	xx	x	xx	x	xx
	Not Reported	x	xx	x	xx	x	xx	x	xx	x	xx	x	xx	x	xx	x	xx	x	xx	x	xx
Vomiting	None	x	xx	x	xx	x	xx	x	xx	x	xx	x	xx	x	xx	x	xx	x	xx	x	xx
	Mild	x	xx	x	xx	x	xx	x	xx	x	xx	x	xx	x	xx	x	xx	x	xx	x	xx
	Moderate	x	xx	x	xx	x	xx	x	xx	x	xx	x	xx	x	xx	x	xx	x	xx	x	xx
	Severe	x	xx	x	xx	x	xx	x	xx	x	xx	x	xx	x	xx	x	xx	x	xx	x	xx
	Not Reported	x	xx	x	xx	x	xx	x	xx	x	xx	x	xx	x	xx	x	xx	x	xx	x	xx
Diarrhea	None	x	xx	x	xx	x	xx	x	xx	x	xx	x	xx	x	xx	x	xx	x	xx	x	xx
	Mild	x	xx	x	xx	x	xx	x	xx	x	xx	x	xx	x	xx	x	xx	x	xx	x	xx
	Moderate	x	xx	x	xx	x	xx	x	xx	x	xx	x	xx	x	xx	x	xx	x	xx	x	xx
	Severe	x	xx	x	xx	x	xx	x	xx	x	xx	x	xx	x	xx	x	xx	x	xx	x	xx
	Not Reported	x	xx	x	xx	x	xx	x	xx	x	xx	x	xx	x	xx	x	xx	x	xx	x	xx
Eye Pruritus	None	x	xx	x	xx	x	xx	x	xx	x	xx	x	xx	x	xx	x	xx	x	xx	x	xx
	Mild	x	xx	x	xx	x	xx	x	xx	x	xx	x	xx	x	xx	x	xx	x	xx	x	xx
	Moderate	x	xx	x	xx	x	xx	x	xx	x	xx	x	xx	x	xx	x	xx	x	xx	x	xx
	Severe	x	xx	x	xx	x	xx	x	xx	x	xx	x	xx	x	xx	x	xx	x	xx	x	xx
	Not Reported	x	xx	x	xx	x	xx	x	xx	x	xx	x	xx	x	xx	x	xx	x	xx	x	xx

Table 43: Number and Percentage of Subjects Experiencing Solicited Events by Symptom, Severity and Day Post First Vaccination – M2SR Recipients, Safety Population (Continued)

Symptom	Severity	Pre-Dose		Post-Dose		Day 1		Day 2		Day 3		Day 4		Day 5		Day 6		Day 7		Day 8+		
		n	%	n	%	n	%	n	%	n	%	n	%	n	%	n	%	n	%	n	%	
Eye Redness (Conjunctivitis)	None	x	xx	x	xx	x	xx	x	xx	x	xx	x	xx	x	xx	x	xx	x	xx	x	xx	
	Mild	x	xx	x	xx	x	xx	x	xx	x	xx	x	xx	x	xx	x	xx	x	xx	x	xx	
	Moderate	x	xx	x	xx	x	xx	x	xx	x	xx	x	xx	x	xx	x	xx	x	xx	x	xx	
	Severe	x	xx	x	xx	x	xx	x	xx	x	xx	x	xx	x	xx	x	xx	x	xx	x	xx	
	Not Reported	x	xx	x	xx	x	xx	x	xx	x	xx	x	xx	x	xx	x	xx	x	xx	x	xx	
Allergy	None	x	xx	x	xx	x	xx	x	xx	x	xx	x	xx	x	xx	x	xx	x	xx	x	xx	
	Mild	x	xx	x	xx	x	xx	x	xx	x	xx	x	xx	x	xx	x	xx	x	xx	x	xx	
	Moderate	x	xx	x	xx	x	xx	x	xx	x	xx	x	xx	x	xx	x	xx	x	xx	x	xx	
	Severe	x	xx	x	xx	x	xx	x	xx	x	xx	x	xx	x	xx	x	xx	x	xx	x	xx	
	Not Reported	x	xx	x	xx	x	xx	x	xx	x	xx	x	xx	x	xx	x	xx	x	xx	x	xx	
Wheezing	None	x	xx	x	xx	NA	NA	NA	NA	NA	NA	NA	NA	NA	NA	NA	NA	NA	NA	NA	x	xx
	Mild	x	xx	x	xx	NA	NA	NA	NA	NA	NA	NA	NA	NA	NA	NA	NA	NA	NA	NA	x	xx
	Moderate	x	xx	x	xx	NA	NA	NA	NA	NA	NA	NA	NA	NA	NA	NA	NA	NA	NA	NA	x	xx
	Severe	x	xx	x	xx	NA	NA	NA	NA	NA	NA	NA	NA	NA	NA	NA	NA	NA	NA	NA	x	xx
	Not Reported	x	xx	x	xx	NA	NA	NA	NA	NA	NA	NA	NA	NA	NA	NA	NA	NA	NA	NA	x	xx
Local Symptoms																						
Any Local Symptom	None	x	xx	x	xx	x	xx	x	xx	x	xx	x	xx	x	xx	x	xx	x	xx	x	xx	
	Mild	x	xx	x	xx	x	xx	x	xx	x	xx	x	xx	x	xx	x	xx	x	xx	x	xx	
	Moderate	x	xx	x	xx	x	xx	x	xx	x	xx	x	xx	x	xx	x	xx	x	xx	x	xx	
	Severe	x	xx	x	xx	x	xx	x	xx	x	xx	x	xx	x	xx	x	xx	x	xx	x	xx	

Table 43: Number and Percentage of Subjects Experiencing Solicited Events by Symptom, Severity and Day Post First Vaccination – M2SR Recipients, Safety Population (Continued)

Symptom	Severity	Pre-Dose		Post-Dose		Day 1		Day 2		Day 3		Day 4		Day 5		Day 6		Day 7		Day 8+	
		n	%	n	%	n	%	n	%	n	%	n	%	n	%	n	%	n	%	n	%
	Not Reported	x	xx	x	xx	x	xx	x	xx	x	xx	x	xx	x	xx	x	xx	x	xx	x	xx
Runny Nose	None	x	xx	x	xx	x	xx	x	xx	x	xx	x	xx	x	xx	x	xx	x	xx	x	xx
	Mild	x	xx	x	xx	x	xx	x	xx	x	xx	x	xx	x	xx	x	xx	x	xx	x	xx
	Moderate	x	xx	x	xx	x	xx	x	xx	x	xx	x	xx	x	xx	x	xx	x	xx	x	xx
	Severe	x	xx	x	xx	x	xx	x	xx	x	xx	x	xx	x	xx	x	xx	x	xx	x	xx
	Not Reported	x	xx	x	xx	x	xx	x	xx	x	xx	x	xx	x	xx	x	xx	x	xx	x	xx
Stuffy Nose/Congestion	None	x	xx	x	xx	x	xx	x	xx	x	xx	x	xx	x	xx	x	xx	x	xx	x	xx
	Mild	x	xx	x	xx	x	xx	x	xx	x	xx	x	xx	x	xx	x	xx	x	xx	x	xx
	Moderate	x	xx	x	xx	x	xx	x	xx	x	xx	x	xx	x	xx	x	xx	x	xx	x	xx
	Severe	x	xx	x	xx	x	xx	x	xx	x	xx	x	xx	x	xx	x	xx	x	xx	x	xx
	Not Reported	x	xx	x	xx	x	xx	x	xx	x	xx	x	xx	x	xx	x	xx	x	xx	x	xx
Sneezing	None	x	xx	x	xx	x	xx	x	xx	x	xx	x	xx	x	xx	x	xx	x	xx	x	xx
	Mild	x	xx	x	xx	x	xx	x	xx	x	xx	x	xx	x	xx	x	xx	x	xx	x	xx
	Moderate	x	xx	x	xx	x	xx	x	xx	x	xx	x	xx	x	xx	x	xx	x	xx	x	xx
	Severe	x	xx	x	xx	x	xx	x	xx	x	xx	x	xx	x	xx	x	xx	x	xx	x	xx
	Not Reported	x	xx	x	xx	x	xx	x	xx	x	xx	x	xx	x	xx	x	xx	x	xx	x	xx
Nasal Pain/Irritation	None	x	xx	x	xx	x	xx	x	xx	x	xx	x	xx	x	xx	x	xx	x	xx	x	xx
	Mild	x	xx	x	xx	x	xx	x	xx	x	xx	x	xx	x	xx	x	xx	x	xx	x	xx
	Moderate	x	xx	x	xx	x	xx	x	xx	x	xx	x	xx	x	xx	x	xx	x	xx	x	xx
	Severe	x	xx	x	xx	x	xx	x	xx	x	xx	x	xx	x	xx	x	xx	x	xx	x	xx

Table 43: Number and Percentage of Subjects Experiencing Solicited Events by Symptom, Severity and Day Post First Vaccination – M2SR Recipients, Safety Population (Continued)

Symptom	Severity	Pre-Dose		Post-Dose		Day 1		Day 2		Day 3		Day 4		Day 5		Day 6		Day 7		Day 8+	
		n	%	n	%	n	%	n	%	n	%	n	%	n	%	n	%	n	%	n	%
	Not Reported	x	xx	x	xx	x	xx	x	xx	x	xx	x	xx	x	xx	x	xx	x	xx	x	xx
Nasal Bleeding/Epistaxis	None	x	xx	x	xx	x	xx	x	xx	x	xx	x	xx	x	xx	x	xx	x	xx	x	xx
	Mild	x	xx	x	xx	x	xx	x	xx	x	xx	x	xx	x	xx	x	xx	x	xx	x	xx
	Moderate	x	xx	x	xx	x	xx	x	xx	x	xx	x	xx	x	xx	x	xx	x	xx	x	xx
	Severe	x	xx	x	xx	x	xx	x	xx	x	xx	x	xx	x	xx	x	xx	x	xx	x	xx
	Not Reported	x	xx	x	xx	x	xx	x	xx	x	xx	x	xx	x	xx	x	xx	x	xx	x	xx
Sinus Pressure/Pain	None	x	xx	x	xx	x	xx	x	xx	x	xx	x	xx	x	xx	x	xx	x	xx	x	xx
	Mild	x	xx	x	xx	x	xx	x	xx	x	xx	x	xx	x	xx	x	xx	x	xx	x	xx
	Moderate	x	xx	x	xx	x	xx	x	xx	x	xx	x	xx	x	xx	x	xx	x	xx	x	xx
	Severe	x	xx	x	xx	x	xx	x	xx	x	xx	x	xx	x	xx	x	xx	x	xx	x	xx
Sore Throat/Sore/Scratchy/Itchy or Painful Throat	Not Reported	x	xx	x	xx	x	xx	x	xx	x	xx	x	xx	x	xx	x	xx	x	xx	x	xx
	None	x	xx	x	xx	x	xx	x	xx	x	xx	x	xx	x	xx	x	xx	x	xx	x	xx
	Mild	x	xx	x	xx	x	xx	x	xx	x	xx	x	xx	x	xx	x	xx	x	xx	x	xx
	Moderate	x	xx	x	xx	x	xx	x	xx	x	xx	x	xx	x	xx	x	xx	x	xx	x	xx
	Severe	x	xx	x	xx	x	xx	x	xx	x	xx	x	xx	x	xx	x	xx	x	xx	x	xx
	Not Reported	x	xx	x	xx	x	xx	x	xx	x	xx	x	xx	x	xx	x	xx	x	xx	x	xx
Cough	None	x	xx	x	xx	x	xx	x	xx	x	xx	x	xx	x	xx	x	xx	x	xx	x	xx
	Mild	x	xx	x	xx	x	xx	x	xx	x	xx	x	xx	x	xx	x	xx	x	xx	x	xx
	Moderate	x	xx	x	xx	x	xx	x	xx	x	xx	x	xx	x	xx	x	xx	x	xx	x	xx

Table 43: Number and Percentage of Subjects Experiencing Solicited Events by Symptom, Severity and Day Post First Vaccination – M2SR Recipients, Safety Population (Continued)

Symptom	Severity	Pre-Dose		Post-Dose		Day 1		Day 2		Day 3		Day 4		Day 5		Day 6		Day 7		Day 8+	
		n	%	n	%	n	%	n	%	n	%	n	%	n	%	n	%	n	%	n	%
	Severe	x	xx	x	xx	x	xx	x	xx	x	xx	x	xx	x	xx	x	xx	x	xx	x	xx
	Not Reported	x	xx	x	xx	x	xx	x	xx	x	xx	x	xx	x	xx	x	xx	x	xx	x	xx
Trouble Breathing/Shortness of Breath	None	x	xx	x	xx	x	xx	x	xx	x	xx	x	xx	x	xx	x	xx	x	xx	x	xx
	Mild	x	xx	x	xx	x	xx	x	xx	x	xx	x	xx	x	xx	x	xx	x	xx	x	xx
	Moderate	x	xx	x	xx	x	xx	x	xx	x	xx	x	xx	x	xx	x	xx	x	xx	x	xx
	Severe	x	xx	x	xx	x	xx	x	xx	x	xx	x	xx	x	xx	x	xx	x	xx	x	xx
	Not Reported	x	xx	x	xx	x	xx	x	xx	x	xx	x	xx	x	xx	x	xx	x	xx	x	xx

Note: N = Number of subjects in the Safety Population who received the specified dose. Severity is the maximum severity reported post dosing for each subject for each day.

Table with similar formatting:

Table 44: Number and Percentage of Subjects Experiencing Solicited Events by Symptom, Severity and Day Post First Vaccination - Placebo Recipients, Safety Population

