Memory Aids: All parent(s)/legal guardian(s) will complete a subject memory aid from the time of the first study vaccination Day 01 (Visit 01) through 7 days after the first study vaccination. Memory aids will be reviewed with the parent(s)/legal guardian(s) for AEs at the clinic visit following receipt of first study vaccination. If a subject noted ongoing local (nasal or injection site) or systemic reactogenicity on the 7th day following the study vaccination (study Day 8), the memory aid will continue to be reviewed until resolved. The memory aids will not be retained as a source document.

Subjects will be observed in the clinic for at least 30 minutes after each study vaccination. Any AE/SAEs will be recorded on the appropriate data collection form prior to discharge from the clinic.

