#### **11.4.2. Primary Safety Data**

Summaries and analysis of safety data will be presented for the Safety Analysis Population.

Solicited AEs will be summarized by severity for each day after the first study vaccination (Days 1-8 post vaccination) and as the maximum severity over all 8 days. Additionally, solicited AEs will be analyzed by taking the most severe response over the follow-up period, dichotomizing into a binary variable (none versus mild, moderate, or severe) and using standard techniques, such as exact confidence intervals, to summarize the number and percentage of subjects reporting each symptom, any upper respiratory symptom and any systemic symptom by treatment arm.

Unsolicited AEs will be coded by Medical Dictionary for Regulatory Activities (MedDRA®) for preferred term and system organ class (SOC). The number of SAEs, AESIs, and NOCMCs is expected to be small in this trial and will be reported by detailed listing showing the event description, MedDRA preferred term and SOC, relevant dates (study vaccinations and AEs), severity, relatedness, and outcome for each event. If more than 5% of subjects report SAEs, and AESIs, and NOCMCs then the number and percentage of subjects reporting each type of event will be reported by treatment arm and compared using Fisher's Exact test. Unsolicited AEs will be summarized as number and percentage of subjects reporting at least one event in each MedDRA preferred term and SOC, cross tabulated by severity and relationship to study product. Additionally, the proportion of subjects and exact 95% confidence intervals of AEs in aggregate and by MedDRA categories will be computed.

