9.3.1. Solicited Events and Symptoms

Systemic and upper respiratory (local) solicited adverse events were collected pre-vaccination, and systemic and local solicited adverse events were collected 30 minutes post-vaccination and then daily for 7 days after first vaccination and graded on a scale of 0 (absent), 1 (mild), 2 (moderate) and 3 (severe). Systemic events include: fever, feverishness (chills/shivering/sweating), fatigue (tiredness), malaise (general unwell feeling), myalgia (body aches/muscular pain), arthralgia (joint pain), headache, flushing, decreased activity, decreased appetite, abdominal pain, nausea, vomiting, diarrhea, eye pruritus, eye redness (conjunctivitis), and allergy. Local events include: runny nose, stuffy nose/congestion, sneezing, nasal pain/irritation, nasal bleeding/epistaxis, sinus pressure/pain, sore throat/sore/scratchy/itchy or painful throat, cough, trouble breathing/shortness of breath. Wheezing experienced on or before Day 8 is considered a solicited event. The grading scales for solicited systemic and local (upper respiratory) adverse events are provided in [Table 7](#) and [Table 6](#), respectively. Grading for wheezing events is provided in [Table 9](#).

The proportion of subjects reporting at least one solicited adverse event will be summarized for each solicited adverse event, any systemic symptom, any local symptom, and any symptoms. The 95% CI calculated using Blaker methodology from a binomial distribution (SAS Proc Freq with a binomial option) will be presented ([Table 40](#)).

For each systemic and local event, any systemic event, any local event, and any solicited event, the maximum severity over 7 days after first vaccination will be summarized for the Safety population. The number and percentage of subjects reporting each event will be summarized by the maximum severity and study group. For each event the denominator is the number of subjects with non-missing data for the specific event ([Table 42](#)).

The number of subjects reporting a solicited adverse event will be summarized for each day post vaccination in a summary table ([Table 43](#) and [Table 44](#)) and graphically in a bar chart ([Figure 50](#) and [Figure 51](#)). The difference proportion of subjects experiencing any individual symptom, any local or systemic symptom, and any symptom overall will be presented in [Table 41](#).

Solicited adverse events by subject will be presented in [Listing 11](#) and [Listing 12](#).

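### Tables 43 and 44 merge study Day 8 with later, selectively reviewed days, and the Table 42 note sets no end day for maximum severity

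*SAP*

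**What the plan says.** Protocol 11.4.2 sets the display: "Solicited AEs will be summarized by severity for each day after the first study vaccination (Days 1-8 post vaccination"), and also "as the maximum severity over all 8 days". Protocol 8.1 sets the collection. Every family keeps the memory aid "from the time of the first study vaccination Day 01 (Visit 01) through 7 days after the first study vaccination", and the same paragraph equates the seventh day after vaccination with study Day 8. If a reaction is still present on that day, "the memory aid will continue to be reviewed until resolved".

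SAP 9.3.1, in the paragraph that cites Table 42, says that "the maximum severity over 7 days after first vaccination will be summarized for the Safety population". SAP 4.5.2 likewise ends solicited events 7 days after vaccination.

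The shells in SAP Appendix 1 read differently. Table 43, and Table 44 in the same format, has columns Pre-Dose, Post-Dose, Day 1 to Day 7, and Day 8+. The Table 42 note reads "Severity is the maximum severity reported over all solicited symptoms post dosing for each subject". The Table 43 note reads "Severity is the maximum severity reported post dosing for each subject for each day". In Table 43 the wheezing row, listed under systemic symptoms, is marked not applicable on Days 1 to 7 and has cells at Pre-Dose, Post-Dose and Day 8+. Protocol 9.2.4 grades wheezing at Visit 02 only. SAP 3.3 treats wheezing as solicited up to Visit 02; SAP 9.3.1 treats it as solicited up to Day 8.

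**The concern.** These displays serve the primary safety objective, and the endpoint ends at about Day 8. A by-day table is useful only if each column covers the same length of time in the same children. Here the last column covers one day for a child who is well on Day 8 and can cover more for a child who is not, so the amount of follow-up depends on the outcome being summarised. An arm with more lingering reactions would have more days over which to take its maximum. Separately, a programmer who works from the Table 42 footnote rather than from SAP 9.3.1 could count a grade that a child first reached after the solicited window had closed.

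**Working it through.** **1. The window.** Take the day of vaccination as Day 1. Seven days after it is Day 1 + 7 = Day 8, so the window is study Days 1 to 8, which is 8 days. This reproduces the protocol's 8 days, and SAP 9.3.1 describes the same window.

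**2. What Table 43 shows.** There are 10 time columns: 2 around dosing, 7 single days, and Day 8+. Of the 8 window days, 7 appear singly and the eighth is merged with whatever follows.

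**3. Direction of the effect.** Let g(d) be a child's grade for a symptom on day d. For a child not reviewed after Day 8, the Day 8+ entry is g(8). For a child reviewed to day k, it is max{g(8), ..., g(k)}, which is at least g(8). Any distortion relative to Day 8 is therefore upward. For a reaction already present on Day 8, continued review cannot change none versus any (Table 40); it can only raise the grade (Table 42).

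**4. The maximum, side by side.**

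| Place | Period for maximum severity |
|---|---|
| Protocol 11.4.2 | 8 days |
| SAP 9.3.1 | 7 days after vaccination, i.e. study Days 1 to 8 |
| SAP Table 42 note | after dosing, no end day |

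**5. Size.** The documents give neither the share of children with a reaction ongoing on Day 8 (q) nor the share of those whose grade rises later (w). Assume q from 10% to 30% and w from 0 to 30%. The expected number moved up a grade per arm is 25 × q × w.

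| q | w = 0 | w = 10% | w = 30% |
|---|---|---|---|
| 10% | 0 | 0.25 | 0.75 |
| 20% | 0 | 0.50 | 1.50 |
| 30% | 0 | 0.75 | 2.25 |

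The range is 0 to 2.25 children per arm; 2.25/25 = 9 percentage points at the top.

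**6. Wheeze cut-off.** Protocol 7.4.1 puts Visit 02 at 7±1 days after vaccination. That is 1 + 6, 1 + 7 or 1 + 8: study Day 7, 8 or 9. Wheeze found at a Day 7 visit meets a cell marked not applicable. Wheeze found at a Day 9 visit is solicited under SAP 3.3 and not under SAP 9.3.1.

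**7. Day numbering.** If Day 1 in Table 43 means one day after vaccination, Day 7 is study Day 8 and Day 8+ lies wholly outside the window. The wheeze row points away from this: Visit 02 is nominally 7 days after vaccination, yet the graded cell sits under Day 8+, which fits Day 1 being the day of vaccination. The SAP is not consistent elsewhere: for unsolicited events, SAP 9.3.2 divides at Days 1-8 and later, while Table 45 uses Days 1-7 and 8-21.

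**The case against.** The best defence is that the text already governs. SAP 9.3.1 and 4.5.2 both give the end day, and the Table 42 note speaks of solicited symptoms, so it can be read inside that definition as a counting rule only. The reading of Day 1 as the day after vaccination also has support: Table 43 is titled by day after vaccination, has separate columns around dosing, and SAP 9.3.1 describes those assessments followed by 7 daily ones. On that reading Day 8+ is already a separate after-window column. Finally, Protocol 8.1 promises continued review, not daily grades entered for analysis. Appendix A schedules memory-aid review only at Visit 02, or at early-termination and unscheduled visits within 8 days.

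Much of this stands as a limit on size. It does not clear the shells: the footnote still differs from the text, and the other numbering conflicts with the wheeze row and leaves a last column outside the window.

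A reader might infer more than the documents support:

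- **That maximum severity misses part of Days 1 to 8.** It does not. Read literally, the note covers the whole window and may overrun it.
- **That Day 8 is seen only in children with symptoms.** Every memory aid runs through study Day 8; selective review starts afterwards.
- **That wheeze is left out.** It has its own row in Tables 40 to 43, and the gaps on Days 1 to 7 match grading at a clinic visit.
- **That Figures 50 and 51 will show a false late rise.** Their implementation note gives a study-day axis without mention of Day 8+, and the figures are not shown.

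**Conclusion.** The point holds as a minor conflict between shells and text in primary safety displays. With Day 1 as the day of vaccination, Tables 43 and 44 do not produce the Day 8 summary that Protocol 11.4.2 requires, and their last column can only be inflated relative to Day 8. The Table 42 note conflicts with SAP 9.3.1 and the protocol, and would admit out-of-window grades if followed literally. The effect is probably small: it needs grades after Day 8 to be recorded and to exceed the earlier maximum, and the illustrative range starts at zero and rests wholly on assumed inputs. The wheeze cut-off is a separate inconsistency within the SAP that could reclassify an event found at a Day 9 visit.

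**What to change.** 1. State in the SAP that Day 1 is the day of vaccination, and apply that count to Tables 42 to 45.
2. In Tables 43 and 44, split Day 8+ into Day 8 and a descriptive column for ongoing events after Day 8.
3. End the maximum in Table 42 at study Day 8 and correct its note to match SAP 9.3.1. End the counts in Tables 40 and 41 at the same day, so that a new symptom reported during extended review of another cannot enter.
4. Reconcile the solicited-wheeze cut-off in SAP 3.3 and 9.3.1, given that Visit 02 can fall on study Days 7 to 9.
5. Footnote in Tables 43 and 44 that wheeze is assessed only at clinic visits, so the by-day composites include it only on those days.

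These are shell and footnote edits. No new data are needed: Listings 11 and 12 already carry the day after vaccination for each solicited record.
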